The dermatology clinics located in: King Abdullah University Hospital (KAUH), in Princess Basma Hospital, (PBH), King Talal Hospital (KTH), Princess Haya Hospital (PHH) and Prince Rashid Hospital (PRH) and King Hussein Medical Center will be visited for patients interview and data collection. The participants' privacy will be preserved throughout the study and the participants' answers will be kept strictly confidential and never associated with any personal details. This study does not involve any human biological sample. No potential risks will be associated with the participation in the current study. No special safety consideration for isotretinoin drug Except those mentioned above since it approved from 1982. Consent will be obtained from IRB.

Data analysis

After data was collected, the data was entered into Excel worksheets. The responses were coded and entered into SPSS (version 23). Descriptive statistics of categorical and continuous variables were

calculated. For the categorical variables, the frequency and percentage were calculated, while the arithmetic mean and standard deviation were calculated for continuous variables.

The differences in participants' responses were examined using the Chi-square test (between intervention and control groups) and McNamara's test (between baseline and follow up encounters) for categorical dependent variables as appropriate. For continuous dependent variables, One Way Analysis of Variance (ANOVA) test, independent samples t-test, and Wilcoxon test were performed when applicable. Both Kolmogorov-Smirnov Z and Shapiro-Wilk tests were used to test for normality of continuous variables. The statistical significance level was considered at a p-value ≤ 0.05 .

Patients Knowledge and Awareness of Isotretinoin:

The degree of knowledge and awareness of correct practice was calculated as a total score. The patient knowledge section consisted of ten different questions/items, and each item had two answers (yes/no). Items were coded according to the answer; the correct (adequate) answer was coded as one (1), while the wrong (not adequate) answer was coded as zero (0). So, the knowledge score could take the values of 0 (no knowledge) to 10 (perfect knowledge).

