Chi square test was used to measure patients' knowledge regarding isotretinoin use at baseline between intervention and control group. It was also used to measure patients' knowledge regarding isotretinoin use at follow-up between intervention and control group. To measure if there was a significant difference in the correct patient knowledge regarding isotretinoin use, the percentage of the correct response for each question was calculated for both groups in baseline and at follow-up. McNamara's test was performed to test if there was a significant difference in knowledge before the intervention and after the intervention in the intervention group, and at if there was a significant difference in knowledge between baseline and follow-up in the control group. In addition, independent t-test was used to compare the knowledge score differences (knowledge score at follow up – knowledge score at baseline) between the intervention group and the control group. Linear regression was conducted to evaluate the effect of the educational intervention on the difference in knowledge score adjusting to variables that were unbalanced at baseline.

Patients Adherence to the Recommendations

Similarly, adherence to recommendations for appropriate uses provided by clinical pharmacists for correct practice was calculated as a total score for each participant. This section consisted of 10 items for all patients, and each item had answers (yes/no). Items were coded according to the answer; the correct (adherent) answer was coded as one (1), while the wrong (not adherent) answer was coded as

zero (0). The adherence score of patients 'compliance with the recommendations ranged between 0 (least adherent) to 10 (most adherent). Average score was evaluated across the intervention and control groups (using t test).

HADS Scale

HADS questionnaire was analyzed based on the scoring system; which consists of fourteen items; seven items each for the depression and anxiety subscale. The score for each item ranges from 0 to 3, and the HADS score ranged from 0 to 21 for depression and the same applied for anxiety.

Chi square test was used to compare HADS items at baseline between intervention and control group. Besides, it was used to compare HADS items at follow-up between intervention and control group. Independent t-test was used to compare the HADS score differences (between baseline and at follow up) between the intervention group and the control group.

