3 months follow-up, and responses of the patients are shown in **Table 2** and **Table 3**; respectively. Patients' average knowledge score at the first meeting before the education process was 6.5 out of 10. There was no significant difference in overall knowledge score at baseline between the intervention group and the control group with a mean (6.47 for the intervention group vs. 6.57 for the control group).. In contrast, the patient's average knowledge score at follow-up (three months after the education session) was 8.22 out of 10. The results at follow-up showed a significant difference in the knowledge score (P-value<0.001) between the intervention (9.3) and control group (7.1).

The average difference in the overall knowledge score (before and after the education process) was statistically different between the intervention and control group (1.6995 ± 1.589 ; P-value< 0.001). The average difference in overall knowledge score was, 2.835 ± 1.329 for the intervention group and 0.530 ± 0.784 for the control group.

Since the monthly income was significantly different between intervention group and control group at baseline, results from linear regression showed that the difference in overall knowledge score is still significantly different between the intervention and control group after adjustment for income status (Coef. = 2.308446); P-value< 0.001

Table 2: Patients knowledge regarding the use of isotretinoin at baseline

	Intervention group n (%)	Control group n (%)	P-value
knowledge about common side effects			
yes	6 (5.8)	2 (2)	0.28
no	97 (94.2)	98 (98)	
We can use isotretinoin during pregnancy*			
yes	10 (9.7)	10 (10)	0.944
no	93 (90.3)	90 (90)	
We can use the drug without prescription*			
yes	6 (5.8)	5 (5)	0.795
no	97 (94.2)	95 (95)	
No need to have laboratory monitoring during isotretinoin use*			
yes	4 (3.9)	5 (5)	0.745
no	99 (96.1)	95 (95)	
We should drink water to reduce the dryness			
yes	99 (96.1)	98 (98)	0.683
no	4 (3.9)	2 (2)	
We should use sunblock to reduce sensitivity to the sun			
yes	99 (96.1)	99 (99)	0.121
no	4 (3.9)	1 (1)	
It is preferred to take isotretinoin with fatty foods			
yes	70 (68)	74 (74)	0.343

no	33 (32)	26 (26)	
We can donate blood during isotretinoin*			
yes	67 (65)	70 (70)	0.451
no	36 (35)	30 (30)	
Woman can lactate while using isotretinoin*			
yes	72 (69.9)	72 (72)	0.742
no	31 (30.1)	28 (28)	
We can make laser or wax during isotretinoin*			
yes	66 (64.1)	55 (55)	0.188
no	37 (35.9)	45 (45)	

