The correct answer is yes unless otherwise indicated. * The correct answer is no.

Table 3: Patients knowledge regarding the use Isotretinoin at follow-up

	Intervention group-post n (%)	Control group- post n (%)	P value
knowledge about common isotretinoin side effects			
yes	49 (47.6)	3 (3)	< 0.001
no	54 (52.85)	97 (97)	
We can use isotretinoin during pregnancy*			
yes	0 (0)	4 (4)	0.057
no	103 (100)	96 (96)	
We can use the drug without prescription*			
yes	0 (0)	5 (5)	0.028
no	103 (100)	95 (95)	
No need to have laboratory monitoring during isotretinoin use*			
yes	0 (0)	5 (5)	0.028
no	103 (100)	95 (95)	
We should drink water to reduce the dryness			
yes	100 (97.1)	98 (98)	0.675
no	3 (2.9)	2 (2)	
we should use sunblock to reduce sensitivity to the sun			
yes	103 (100)	99 (99)	0.493
no	0 (0)	1 (1)	
It is preferred to take isotretinoin with fatty foods			
yes	103 (100)	81 (81)	< 0.001
no	0 (0)	19 (19)	
We can donate blood during isotretinoin*			
yes	0 (0)	57 (57)	< 0.001
no	103 (100)	43 (43)	
Woman can lactate while using isotretinoin*			
yes	9 (8.7)	60 (60)	< 0.001
no	94 (91.3)	40 (40)	
We can make laser or wax during isotretinoin*			

yes	5 (4.9)	40 (40)	< 0.001
no	98 (95.1)	60 (60)	

The correct answer is yes unless otherwise indicated. * The correct answer is no.

The percent of correct answers were significantly higher at follow up compared to baseline for most of knowledge questions in the intervention group. On the other hand, the percent of correct answers were significantly higher at follow up compared to baseline for the five out of the ten knowledge questions in the control group as shown in **Table 4**.

Table 4: Patient knowledge regarding isotretinoin use at baseline and at follow up.

	Intervention group- baseline n (%)	Intervention group- follow up n (%)	P -value	Control group- baseline n (%)	Control group- follow up n (%)	P-value
knowledge about common isotretinoin side effects						
	6 (5.8)	49 (47.6)	< 0.001	2 (2)	3 (3)	0.564
We can use isotretinoin during pregnancy*						
	93 (90.3)	103 (100)	0.0016	90 (90)	96 (96)	0.0339
We can use the drug without prescription*						
	97 (94.2)	103 (100)	0.0143	95 (95)	95 (95)	0.95
No need to have laboratory monitoring during isotretinoin use*						
	99 (96.1)	103 (100)	0.0455	95 (95)	95 (95)	0.95
We should drink water to reduce the dryness						
	99 (96.1)	100 (97.1)	0.705	98 (98)	98 (98)	0.98
we should use sunblock to reduce sensitivity to the sun						

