	99 (96.1)	103 (100)	0.045	99 (99)	99 (99)	0.317
It is preferred to take isotretinoin with fatty foods						
	70 (68)	103 (100)	< 0.001	74 (74)	81 (81)	0.0196
We can donate blood during isotretinoin*						
	36 (35)	103 (100)	< 0.001	30 (30)	43 (43)	0.0008
Woman can lactate while using isotretinoin*						
	31 (30.1)	94 (91.3)	< 0.001	28 (28)	40 (40)	0.0027
we can make laser or wax during isotretinoin*						
	37 (35.9)	98 (95.1)	<0.001	45 (45)	60 (60)	0.0011

Frequencies and percentages presented are for correct answers.

At follow-up, patients were asked if they searched for outside sources for information about the drug during their treatment. About 56% of the control group compared to 45% of the intervention group said yes with P-value=0.079.

4. Patient's Adherence to Recommendations About the Proper Use

The patient's adherence to recommendations for the proper use of isotretinoin and the adherence to

specific instructions on managing side effects provided by the physician or clinical pharmacist at follow-up was evaluated. The average recommendation score was 7.601 ± 1.358 for all patients, and it was significantly different between control and intervention group (the mean for intervention group= 8.534 ± 0.905 and control group= 6.64 ± 1.039) with P-value <0.001 . The percentage of participants who were adherent to all recommendations (10 out of 10) was 15.5% for the intervention group compared to 0% for the control group.

The frequency and number for patients who were adherent to the recommendations for the intervention group and control group are summarized in **Table 4.5**. Around 59% of the intervention group compared to 27% of the control group were adherent to drinking plenty of water (more than two liters per day) with P-value <0.001 .

Table 5: Patient's adherence to recommendations about the proper use at follow-up

	Intervention group n (%)	Control group n (%)	P value
I adhere to drink plenty of water during isotretinoin use			
yes	61 (59.2)	27 (27)	< 0.001
no	42 (40.8)	73 (73)	
I adhere to use eye drop during isotretinoin use			
yes	89 (86.4)	69 (69)	0.003
no	14 (13.6)	31 (31)	
I adhere to use lip balm during isotretinoin use			
yes	101 (98.1)	98 (98)	0.90
no	2 (1.9)	2 (2)	
I adhere to use body lotion during isotretinoin use			
yes	48 (46.6)	28 (28)	0.006
no	55 (53.4)	72 (72)	
I adhere to make laboratory monitoring (AST & ALT) during isotretinoin use			
yes	102 (99)	98 (98)	0.618
no	1 (1)	2 (2)	

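### Table 4 applies the uncorrected McNemar chi-square to items with very few discordant pairs: two intervention p-values of about 0.045 are 0.125 by the exact test, and four control p-values do not fit their counts

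*Combined protocol and SAP*

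**What the plan says.** The Data analysis section assigns McNemar's "test (between baseline and follow up encounters) for categorical dependent variables as appropriate" and sets significance at p ≤ 0.05. The subsection on patients' knowledge repeats the choice for each arm: the "test was performed to test if there was a significant difference in knowledge before the intervention and after the intervention". Neither place says whether the test is uncorrected, continuity-corrected, exact or mid-p.

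Results 3 draws two conclusions from Table 4. For the intervention arm: "The percent of correct answers were significantly higher at follow up compared to baseline for most of knowledge questions in the intervention group". For the control arm: "the percent of correct answers were significantly higher at follow up compared to baseline for the five out of the ten knowledge questions". The table's footnote fixes what is counted: "Frequencies and percentages presented are for correct answers". The same section gives baseline mean knowledge scores of "6.47 for the intervention group vs. 6.57 for the control group".

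**The concern.** McNemar's test uses only the discordant pairs, that is, patients whose answer changed from wrong to correct or from correct to wrong. Its chi-square approximation is poor when there are few of them. Several items were answered correctly by 94% or more at baseline, so few patients could improve. An item can then fall below 0.05 through the choice of test version alone.

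The report is also uneven about sparse data. In Table 3 ("Patients knowledge regarding the use Isotretinoin at follow-up"), four sparse between-arm rows carry Fisher exact p-values. For pregnancy this gives 0.057, where chi-square would give 0.040. The exact test removed nominal significance there, while the asymptotic test kept it for two items in Table 4.

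Finally, an unchanged number correct means equal numbers changed in each direction, so the test should show no evidence of change. Table 4 prints 0.317 for one such row and values just below 1 for three others.

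**Working it through.** **Inputs.** Counts correct and p-values come from Table 4 (103 intervention, 100 control). Let b be the patients going from wrong to correct and c those going from correct to wrong; b − c is the change in the number correct. All tests are taken as two-sided.

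**Formulas.** Uncorrected: (b − c)²/(b + c) on 1 df. Exact: two-sided binomial with n = b + c and probability 0.5. Mid-p (for b ≠ c): exact p minus the probability of the observed split.

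**Step 1: rows where the pairs are known.** If all 103 are correct at follow-up, then c = 0 and b = 103 − baseline. For laboratory monitoring and sunblock, b = 103 − 99 = 4. Uncorrected: 4²/4 = 4.0, p = 0.0455. This is the printed 0.0455, and the printed 0.045 truncated. Exact: 2 × 0.5⁴ = 0.125. Mid-p: 0.125 − 0.0625 = 0.0625. With four pairs a two-sided exact test cannot go below 0.125.

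**Step 2: rows where the pairs are inferred.** All splits with the printed net change were searched. One split per row reproduces the printed p under the uncorrected formula.

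| Arm, item | Counts | b/c | Printed | Uncorrected | Exact | Mid-p |
|---|---|---|---|---|---|---|
| Int., laboratory | 99→103 | 4/0 known | 0.0455 | 0.0455 | 0.125 | 0.0625 |
| Int., sunblock | 99→103 | 4/0 known | 0.045 | 0.0455 | 0.125 | 0.0625 |
| Int., prescription | 97→103 | 6/0 known | 0.0143 | 0.0143 | 0.031 | 0.016 |
| Int., pregnancy | 93→103 | 10/0 known | 0.0016 | 0.0016 | 0.002 | 0.001 |
| Int., water | 99→100 | 4/3 inferred | 0.705 | 0.705 | 1.0 | 0.727 |
| Ctl., side effects | 2→3 | 2/1 inferred | 0.564 | 0.564 | 1.0 | 0.625 |
| Ctl., pregnancy | 90→96 | 7/1 inferred | 0.0339 | 0.0339 | 0.070 | 0.039 |
| Ctl., fatty foods | 74→81 | 8/1 inferred | 0.0196 | 0.0196 | 0.039 | 0.021 |
| Ctl., blood donation | 30→43 | 14/1 inferred | 0.0008 | 0.0008 | 0.001 | 0.0005 |
| Ctl., lactation | 28→40 | 14/2 inferred | 0.0027 | 0.0027 | 0.004 | 0.0023 |
| Ctl., laser/wax | 45→60 | 18/3 inferred | 0.0011 | 0.0011 | 0.0015 | 0.0009 |

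The other five intervention items have at least 33 discordant pairs each and stay below 0.001 under any version.

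**Step 3: control rows with equal counts.** Prescription (95→95), laboratory monitoring (95→95), water (98→98) and sunblock (99→99) all force b = c. Uncorrected and exact p are then 1, or undefined with no discordant pairs. Mid-p would lie between 0.50 and 0.75. None of these gives 0.95, 0.95, 0.98 or 0.317. The first three coincide with the proportions correct.

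**Step 4: the control sunblock count.** Table 2 prints 4 intervention and 1 control patient wrong at baseline on "We should use sunblock to reduce sensitivity to the sun". Several figures point to 0 control patients wrong, that is, 100 correct:

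- 0.317 is the uncorrected p for one discordant pair (1/0: chi-square 1.0).
- Table 2 prints p = 0.121. Fisher for 4/103 vs 0/100 is 0.1215; for the printed 4/103 vs 1/100 it is 0.369 (chi-square 0.185).
- The printed control baseline counts sum to 2+90+95+95+98+99+74+30+28+45 = 656, a mean of 6.56. The stated 6.57 needs 657.
- Control follow-up counts sum to 710. The stated change of 0.530 needs 710 − 657 = 53; the printed counts give 54.
- The pooled change is stated as 1.6995. The intervention total is 959 − 667 = 292, and (292 + 53)/203 = 1.6995. With 54 it would be 1.7044.

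**Step 5: Table 3 for comparison.** Numbers wrong, intervention vs control, Fisher then chi-square: pregnancy 0 vs 4, 0.057 and 0.040 (printed 0.057); prescription and laboratory monitoring 0 vs 5, 0.0275 and 0.0216 (printed 0.028 for both); sunblock 0 vs 1, 0.493 and 0.309 (printed 0.493). These four rows are Fisher.

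**The case against.** The arithmetic is not in dispute; the objections concern scope and weight.

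- **Only some rows are sparse.** True: five intervention rows are safe under any version, and the point is confined to the others.
- **Table 3 is not a clean contrast.** Also true. Its water row (3 vs 2 wrong) prints 0.675, the chi-square value, where Fisher gives 1.0. So the report is inconsistent within Table 3 as well, and the plan names only chi-square for those comparisons. This adds to the inconsistency.
- **The plan names no version, so this is not a departure from it.** Correct. It is an under-specified test run with a version unsuited to four pairs.
- **Exact versus mid-p is partly preference.** This matters for one row, control pregnancy (0.070 or 0.039), and so for the control count of five. It does not matter for the two 4/0 rows, which lose significance under both.
- **The origin of 0.95 and 0.98 is guesswork.** Fair. Table 9 prints 0.99 for two rows shown as 100% adherent in both arms, so these may be placeholders for no difference and not copied proportions. They need replacing either way.
- **The sunblock count may be the error, not its p-value.** This is the likelier reading, but only source data can settle it.
- **The effect is small.** Agreed: these are within-arm, item-level tests.

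**Conclusion.** The concern holds. Two intervention p-values cross the plan's 0.05 threshold only through the test version, and this rests on pair counts that the table itself fixes. Intervention items at p ≤ 0.05 fall from 9 to 7 of 10, so the statement about most items survives. For the control arm, five significant items become four under the exact test and remain five under mid-p; this rests on splits inferred from the printed p-values. That the uncorrected version was used is also an inference, but it reproduces every numerically printed p-value except those of the four equal-count control rows. In each of those four rows the p-value or the count is wrong; for sunblock the evidence favours a baseline count of 100.

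The between-arm total-score results (knowledge change 2.835 vs 0.530; adherence score 8.534 vs 6.64) are unaffected. The correction should be made, but the trial's main findings do not depend on it.

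**What to change.** 1. State in the Data analysis section that within-arm item comparisons use the exact binomial McNemar test or its mid-p version, and name which.
2. Recompute all 20 p-values in Table 4 from the patient-level pairs, not from the printed margins, and report b and c for each item.
3. Replace 0.95, 0.95 and 0.98 in the control column. Check the control sunblock baseline count against source data and correct Tables 2 and 4 accordingly.
4. Make the sentence on control items agree with the recomputed table: four items if exact and five if mid-p, provided the inferred splits are confirmed.
5. Label the within-arm and item-level tests as descriptive and unadjusted for multiplicity, with the education effect resting on the between-arm comparisons already in the plan. No primary outcome should be named now that results are known.

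The cost is re-running one test on existing data, checking one count, and editing one sentence and up to 20 table cells. Two intervention items lose nominal significance, and one control item does so if the exact version is chosen.

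### Item-level knowledge gains are tested within each arm and the counts of significant items are set against each other; this is not a test of the education, although the total-score result is unaffected

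*Combined protocol and SAP*

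**What the plan says.** The knowledge subsection of Data analysis plans McNemar's test (the name is misprinted there) separately by arm. In the intervention arm it serves "to test if there was a significant difference in knowledge before the intervention and after the intervention in the intervention group". In the control arm it asks "if there was a significant difference in knowledge between baseline and follow-up in the control group". Under Table 4, Results section 3 reports that correct answers were "significantly higher at follow up compared to baseline for most of knowledge questions in the intervention group". It then turns to the controls, where "the percent of correct answers were significantly higher at follow up compared to baseline for the five out of the ten knowledge questions".

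The same subsection also plans three comparisons that do use the randomised arms:

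- a chi-square test of "knowledge regarding isotretinoin use at follow-up between intervention and control group", item by item (Table 3);
- for the total score, "independent t-test was used to compare the knowledge score differences" between arms;
- for the same change score, "Linear regression was conducted to evaluate the effect of the educational intervention on the difference in knowledge score", adjusted for variables unbalanced at baseline.

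On the threshold, the text says "The statistical significance level was considered at a p-value ≤ 0.05". Sidedness is not stated, and I assume two-sided tests.

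**The concern.** A change from baseline within one arm mixes the education with everything else that happens over three months: repeat questioning, time on treatment, and the physician's advice, which both arms receive. Only the comparison with controls separates these. A significant result in one arm beside a non-significant one in the other, or a higher count of significant items, is not a test of the difference between arms.

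The reading can mislead in both directions. It can make an item look like a success of the education when controls improved almost as much. It can also suggest that the education added nothing on items where both arms improved but the intervention arm improved far more. At stake is what the trial says about individual recommendations, including the pregnancy item.

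**Working it through.** **1. Total score first.** Inputs from Results section 3: mean change 2.835 (SD 1.329, n = 103) v 0.530 (SD 0.784, n = 100).

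- Difference = 2.835 − 0.530 = 2.305.
- SE = √(1.329²/103 + 0.784²/100) = 0.153.
- 95% CI = 2.305 ± 1.96 × 0.153 = 2.01 to 2.60; Welch t = 15.1, P < 0.001.

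This agrees with the printed P < 0.001 and the income-adjusted coefficient of 2.308. The 1.6995 printed in the same paragraph is the mean change over all 203 patients, (103 × 2.835 + 100 × 0.530)/203, not the difference between arms.

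**2. Items.** Gains are percentage points in correct answers from the Table 4 counts, with denominators 103 and 100. Within-arm P-values are from Table 4 and between-arm P-values at follow-up from Table 3.

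| Item | Gain, intervention (P) | Gain, control (P) | Net gain | Between-arm P |
|---|---|---|---|---|
| Side effects | 41.7 (<0.001) | 1.0 (0.564) | 40.7 | <0.001 |
| Pregnancy | 9.7 (0.0016) | 6.0 (0.0339) | 3.7 | 0.057 |
| Prescription | 5.8 (0.0143) | 0 (0.95) | 5.8 | 0.028 |
| Laboratory tests | 3.9 (0.0455) | 0 (0.95) | 3.9 | 0.028 |
| Water | 1.0 (0.705) | 0 (0.98) | 1.0 | 0.675 |
| Sunblock | 3.9 (0.045) | see step 5 | see step 5 | 0.493 |
| Fatty food | 32.0 (<0.001) | 7.0 (0.0196) | 25.0 | <0.001 |
| Blood donation | 65.0 (<0.001) | 13.0 (0.0008) | 52.0 | <0.001 |
| Breastfeeding | 61.2 (<0.001) | 12.0 (0.0027) | 49.2 | <0.001 |
| Laser/wax | 59.2 (<0.001) | 15.0 (0.0011) | 44.2 | <0.001 |

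At P ≤ 0.05 the counts are 9 of 10 within the intervention arm, 5 of 10 within control, and 7 of 10 between arms. Fatty food, blood donation, breastfeeding and laser/wax are significant in both arms, yet they have large net gains and between-arm P < 0.001.

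**3. Pregnancy.** Intervention went from 93 to 103 of 103, so there were exactly 10 gains and no losses: McNemar χ² = 10²/10 = 10, P = 0.0016, as printed. Control went from 90 to 96 of 100, net 6. The printed P = 0.0339 corresponds to χ² = 4.5, so discordant pairs = 36/4.5 = 8, that is 7 gains and 1 loss.

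- Net gain = 10/103 − 6/100 = 0.037.
- Variance = (0.0971 − 0.0971²)/103 + (0.08 − 0.06²)/100 = 0.00085 + 0.00076; SE = 0.040.
- 95% CI = −4.2 to 11.6 points.

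**4. Which test gives P = 0.057.** Follow-up wrong answers are 0 of 103 v 4 of 100. Fisher's exact test gives 0.057, uncorrected chi-square 0.040, and continuity-corrected chi-square 0.122. Expected wrong answers are about 2 per arm (4 × 103/203 = 2.03), so the exact test is the sound choice, and it is the one that matches the table. With uncorrected chi-square throughout, the between-arm count would be 8.

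**5. Sunblock.** Table 4 prints control as 99 to 99 of 100 with P = 0.317. No net change gives χ² = 0, whereas P = 0.317 means χ² = 1, which fits one net change. As printed, the net gain is 3.9 points and its Wald interval just excludes zero (P = 0.04). If control went from 100 to 99, the net gain is 4.9 points (95% CI 0.7 to 9.1). The example cannot be used until the counts are settled.

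**The case against.** The strongest reply is that the plan already contains the right comparisons. The change-score t-test and the regression are specified in the two sentences after the McNemar tests, and Table 3 gives a between-arm test for all ten items. The text draws no effect size and no conclusion about the education from the counts, and it openly reports that controls improved on five items. Paired tests beside randomised comparisons are a common description. On pregnancy, both arms are significant, so contrasting significance would not by itself suggest a difference; the net gain is also limited by a ceiling, since the intervention arm reached 103 of 103.

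Most of this stands, and it rules out a stronger inference. A reader might conclude that the knowledge effect is inflated by the 0.53 points that controls gained, 19% of the intervention arm's 2.835. The documents do not support that, because both total-score analyses subtract the control gain. Nor do they contain a narrative claim about pregnancy or sunblock that could be called wrong.

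What remains is narrower. The results place the two counts in explicit opposition, and the pregnancy row, read down the intervention column, looks like an effect that the randomised comparison does not establish. Table 3 ignores the baseline answer, McNemar ignores the other arm, and the regression covers only the total score. So no planned item-level analysis uses both arm and baseline, and no item has an estimate with a confidence interval.

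**Conclusion.** The point holds at item level only, and it is minor. The contrast of significant-item counts is not evidence of an education effect. It disagrees with the between-arm tests in both directions: pregnancy looks established within the intervention arm but not between arms (net 3.7 points, 95% CI about −4.2 to 11.6), and four items that look alike across arms differ by 25 to 52 points. Item-level interpretation changes; the overall conclusion (2.305 points, 95% CI 2.01 to 2.60) does not.

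This rests on the printed counts, on two-sided tests, on control discordant pairs inferred from a rounded P-value, and on a large-sample interval with few events. An interval that includes zero does not show that the education had no effect on the pregnancy item. Paired item data are not given, so baseline-adjusted estimates cannot be computed from the documents.

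**What to change.** - Delete the two sentences under Table 4 that set the counts of significant items against each other.
- Label Table 4 descriptive. The baseline and follow-up percentages can stay; the within-arm P-values should not be cited as evidence of effect.
- Base every item statement on the between-arm comparison. For each item, report the difference in percentage correct at follow-up, adjusted for the same item at baseline, with a 95% CI. Several cells are at 0% or 100%, so use a method that tolerates them, such as a risk difference stratified by baseline answer with a score-type interval, or penalised logistic regression.
- State that item tests with small expected counts use Fisher's exact test, as Table 3 appears to do.
- Reconcile the control sunblock counts with P = 0.317 before interpreting that item.

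The cost is a re-analysis of ten items from data in hand, two sentences and one table. No new data are needed, and the total-score result stays as it is.
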